#### RECIST 1.1 criteria

- i. Compared to baseline\* (or lowest sum while on study if less than baseline), a 20% increase in the sum of the diameters of baseline target lesions with an absolute increase of at least 5 mm, or
- ii. Any new lesions (measurable or non-measurable), or
- iii. Unequivocal increase in non-target disease, defined as an overall level of substantial worsening in non-target disease such that the overall tumor burden merits discontinuation of therapy.

#### Gynecological Cancer Intergroup criteria

- i. Patients with elevated CA-125 pretreatment and normalization of CA-125 must show evidence of CA-125 greater than, or equal to, 2 times the upper limit of the reference range on 2 occasions at least 1 week apart, or
- ii. Patients with elevated CA-125 before treatment, which never normalizes, must show evidence of CA-125 greater than, or equal to, 2 times the nadir value on 2 occasions at least 1 week apart, or
- iii. Patients with CA-125 in the reference range before treatment must show evidence of CA-125 greater than, or equal to, 2 times the upper limit of the reference range on 2 occasions at least 1 week apart.

- (3) At the final 18-month post-implantation time point.

\* Baseline is defined as the follow-up time point following completion of chemotherapy treatment.

Device removal will be performed via minimally invasive surgery (laparoscopy) following the institution's standard protocols. To remove the device, M-Trap device(s) will be located, carefully segregating the device with any captured tumor cells from the surrounding tissues. Next, a single-use specimen retrieval system (Endobag™ container) will be placed to recover the extracted M-Trap device through the 15mm trocar cannula of the laparoscopic port, maintaining the integrity of the device for histological analysis.

The laparoscopy will be completed following the institution's standard protocols. An assessment of the device removal procedure will occur at the time of explant, including ease of locating and removing the M-Trap device and the occurrence of any device- or procedural-related AEs during the removal procedure. If for some reason the device(s) cannot be explanted through laparoscopy, the surgeon should proceed using best clinical judgement, including a potential conversion to laparotomy.

Semi-quantitative scoring of disease focalization based on direct visual assessment, CT scan and ultrasound will be performed at the time of device removal, using the following scale:

Degree of Disease Focalization	Definition
I	Approximately 100% of recurrent disease contained in M-Trap devices
II	Approximately 75% of recurrent disease contained in M-Trap devices
III	Approximately 50% of recurrent disease contained in M-Trap devices
IV	Approximately 25% of recurrent disease contained in M-Trap devices
V	No obvious recurrent disease contained in M-Trap devices

Following device removal, mark the side of the device that faced outward into the peritoneal cavity with an "X" using a surgical suture. Place each explanted device in a separate, labelled container prepared per standard institution protocol. Labels shall include institution name, protocol number (MTRAP-2016-01), study subject identification number, date of explant, and location of explant (i.e., right paracolic gutter, left paracolic gutter, liver). The hospital laboratory must follow Appendix 1 to prepare the explant for shipping to the core laboratory. After standard pathological analysis at the institution, samples shall be shipped following the institution's protocols for shipment of biological samples to the core laboratory for histology evaluation:

[name] / [name]  
 Hospital Arnau de Vilanova, Anatomia Patològica  
 [name]  
 [name]  
 [contact]  
 Email: [contact], [contact]

All patients will be followed through 18 months, regardless of whether or not the device was removed at an earlier time point.

### **6.3. Post-Operative Care**

Post-operative care will follow the institution's standard rehabilitation protocol.

### **6.4. Follow-Up Assessments**

At each follow-up visit at 1 month  $\pm$  1 week, 3 months  $\pm$  2 weeks, 6 months  $\pm$  2 weeks, 9 months  $\pm$  1 month, 12 months  $\pm$  1 month, 15 months  $\pm$  1 month and 18 months  $\pm$  1 month, the patient will undergo the following assessments and tests:

- Conduct physical examination.
- Collect Biomarker CA-125 level. (except at 1 month visit)
- Perform an abdominal ultrasound.
- Perform a CT scan of the abdomen, pelvis, and chest. (except at 1 month visit)
- Record any adverse events.
- Collect concomitant medications information.
- In addition, if device removal is planned:
  - Record data regarding device removal.
  - Perform pathology of the explanted device.

### **6.5. Medication Regimen**

Use of all medications will be recorded in the patient's CRF. This will include all prescription and OTC drugs. Any changes in medications also will be recorded in the patient's CRF.

Any concomitant medication deemed necessary for the welfare of the patient during the study may be given at the discretion of the investigator. However, it is the responsibility of the principal investigator to ensure that details regarding the medication are recorded in full on the CRF.

### **6.6. Summary of Required Assessments**

#### **6.6.1. Demographic Data/Medical History**

Demographic data and a complete medical history will be collected at screening. The medical history will include a complete history of the patient's cancer and any prior treatments. The medical history will be used to ensure that the patient does not meet any of the exclusion criteria. A review of medical history will be conducted at the screening visit.

#### **6.6.2. Physical Examination**

A pre-op general physical examination will occur at the screening visit. A specific pelvic (gynecologic) examination to manually examine the abdomen and pelvic area for any nodules or bumps, as indicated in the CRF, will be conducted at the screening visit and at each follow-up visit.

#### **6.6.3. Biomarker CA-125**

Cancer antigen 125 (CA-125) is best known as a biomarker to monitor epithelial ovarian cancer and for the differential diagnosis of pelvic masses. A CA-125 test measures the amount of the CA-125 in a person's blood. This test can be used to monitor the effectiveness of treatment and cancer recurrence. A CA-125 test will be performed at the screening visit and at each follow-up visit.

#### **6.6.4. CT Scan**

Computed tomography (CT) scan is one of the most commonly used tools for the screening, diagnosis and treatment of cancer. A CT scan is an X-ray procedure that uses a computer to produce three-dimensional, cross-sectional images of inside the body. A CT scan of the abdomen, pelvis, and chest will be performed at the screening visit and at each follow-up visit. Observations based on CT findings will be documented on the CRF with images appended for review and confirmation by the Data Safety Monitoring Board.

#### **6.6.5. Ultrasound**

Ultrasound (US) is a non-invasive method for evaluation of the abdominal cavity. US will be used precisely locate the position of a tumor, monitor M-Trap performance and assess tumor recurrence. Abdominal US will be performed within 24 hours of the implant procedure (post-implant) and at each follow-up visit. Observations based on real-time ultrasound findings will be documented on the CRF with still images appended for review and confirmation by the Data Safety Monitoring Board.

#### **6.6.6. Peritoneal Carcinomatosis Index (PCI)**

The Peritoneal Carcinomatosis Index (PCI) is used to assess the extent of peritoneal cancer throughout the peritoneal cavity. For this purpose, the peritoneal cavity is divided in 13 well-defined regions. In each of the 13 regions, the size of the largest tumor nodule is measured. If no tumor is visualized, a score of "0" is given to that region. If the largest tumor nodule is smaller than 0.5 cm, the score is "1". For tumors measuring between 0.5 cm and 5 cm, the score is "2". For lesions larger than 5 cm, the score is "3". If there is layering or a confluence of multiple small tumor nodules, the score is "3". The PCI is calculated by adding the scores of all 13 regions together with a maximum score of 39 (13×3). Determination of PCI will be made at time of diagnostic laparoscopy (if available) and at time of surgical debulking (pre- and post-procedure).

#### **6.6.7. Pathology**

Pathology analysis will be done on explanted M-Trap devices to evaluate the host tissue response to the device, assess the cellular immune response, and characterize the tumor cells captured by the device.

Each device will be excised, fixed in 10% neutral-buffered formalin, and embedded in paraffin. Tissue samples will be sectioned (3-5 µm), hematoxylin and eosin (H&E) stained and histologically evaluated. Masson Trichrome stain will also be used to evaluate collagen deposition.

Tumor size will be determined by measuring the longest diameter (length) and width. Immunohistochemistry (IH) against CD3, CD20 and CD68 will be performed to assess the cellular immune response. Immunohistochemistry (IH) against CKAE1/AE3, CK7, ER and P53 will be performed to characterize tumor cells captured by the device. Immunohistochemical results will be evaluated semi-quantitatively, by considering percentage of positively stained cells. All the findings will be documented and images from a microscope will be obtained. Advanced analysis may be performed, if available.

### **6.6.8. Cytology/biopsy**

At the time of device removal, additional microscopic data will be collected following a modified, laparoscopic second-look procedure (Gynecologic Oncology Group Surgical Procedures Manual, rev Jan 2010).

Ascites: If ascites are present, a sample will be collected for cytologic assessment.

Peritoneal Washings: If ascites are not present, prior to device removal peritoneal washings will be performed in the following locations:

- a) Pelvis
- b) Right and left paracolic gutters, and
- c) Subdiaphragmatic space.

The three specimens will be combined and analyzed cytologically as a single specimen.

Biopsies: If no visual tumors are seen, a minimum of two (2) biopsies should be obtained from the following locations after device removal and will be analyzed as separate specimens:

- a) Right and left sidewall,
- b) Cul-de-sac and vesical peritoneum,
- c) Right and left abdominal gutter peritoneum,
- d) Undersurface of the right diaphragm,
- e) Residual omentum,
- f) Adhesive bands, abnormally scarred areas, and
- g) Retroperitoneum.

## **6.7. Withdrawals or Discontinuation**

### **6.7.1. Lost to Follow-Up Subject**

A subject will be considered “lost to follow-up” and terminated from the study when all of the following criteria have been met.

- Failure to complete 3 consecutive visits without due cause (after 30 days).
- Documentation of three (3) unsuccessful attempts, one of which must be in written communication, by the Investigator or his/her designee to contact the subject or next of kin.
- A letter from the Investigator to Sponsor reporting subject as lost to follow up.

### **6.7.2. Withdrawal and Replacement of Subjects**

Subjects may withdraw from the study at any time, with or without reason and without prejudice to further treatment. Patients still implanted at the time of intent of withdrawal will undergo the device removal procedure and associated assessments before being exited from the trial. The reason for withdrawal will be recorded (if given) in all cases of withdrawal. The investigator may discontinue a subject from participation in the study if the investigator feels that the subject can no longer fully comply with the requirements of the study or if any of the study procedures are deemed potentially harmful to the subject. Data that have already been collected on withdrawn subjects will be retained and used for analysis but no new data will be collected after withdrawal.

Withdrawn subjects will not be replaced.

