### 6.2.3. Device Removal Procedure

Following completion of chemotherapy treatment, M-Trap devices will be removed under one of following scenarios, whichever occurs first:

- (1) In the event of an adverse event necessitating device removal.
- (2) After disease progression as defined by objective RECIST 1.1 and CA-125 criteria. Both criteria must be met as follows:

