Add 1 to the score if Large bowel resection is ticked (colectomy, rectosigmoid resection).

Add 1 to the score if Diaphragm peritonectomy or Full-thickness diaphragm resection (diaphragm resection) is ticked.

Add 1 to the score if Partial hepatectomy (hepatic resection) is ticked.

- Derived criterion “freedom of device- and procedure-related major adverse events through 6 months post-implantation, including shock, cardiac arrest, myocardial infarction, pulmonary embolism, prolonged intubation, unplanned reintubation, or adverse events leading to removal of the device, including infection, seroma formation, mesh migration, bowel obstruction, adhesions, and local cancer progression through the abdominal wall at M-Trap suture sites” which is the primary endpoint will be calculated as follows:

If a MAE occurred in a patient within 6 months \pm 2W post implantation and “Does this event meet the definition of a major adverse event for the primary endpoint?” = “Yes” then “freedom of device- and procedure-related major adverse events through 6-months post-implantation” = “No” else “freedom of device- and procedure-related major adverse events through 6-months post-implantation” = “Yes”.

- Derived criterion “recurrent patients” will be defined as patients with device removal reason “Disease progression as defined by objective RECIST 1.1 and CA-125 criteria” or device removal reason “other” that indicates recurrence. Derived criteria “non-recurrent patients” are the remaining patients. CRO will send to MTrap an excel file with the list of all other reason of device removal to identify the reason that indicates “recurrence”.
- Derived criterion “time to recurrence” will equal to the date of the follow-up visit when “Device removal planned for this visit” is yes minus the procedure date.
- Derived criterion “platinum resistant, recurrent patients” will be defined as “recurrent patients” where the difference between the date of the follow-up visit when “Device removal planned for this visit” is yes and the date of the most recent chemotherapy medication treatment is less than or equal to 180 days.
- CRO will send to MTrap an excel file with the list of the concomitant medication to identify the chemotherapy medication treatment. Derived criterion “platinum sensitive, recurrent patients” will be defined as “recurrent patients” that are not “platinum resistant, recurrent patients”.

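### Removal on withdrawal is not reconciled with the device-removal rule, and the SAP pools early explants for withdrawal or an adverse event with the month-18 explants as non-recurrent

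*Protocol*

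**What the plan says.** **Protocol, withdrawal.** Section 6.7.2 opens with "Subjects may withdraw from the study at any time, with or without reason and without prejudice to further treatment". It continues: "Patients still implanted at the time of intent of withdrawal will undergo the device removal procedure and associated assessments before being exited from the trial". Data already collected are kept, nothing is collected after withdrawal, and withdrawn subjects are not replaced.

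**Protocol, removal.** Section 6.2.3 begins: "Following completion of chemotherapy treatment, M-Trap devices will be removed under one of following scenarios, whichever occurs first". Three scenarios follow:
- "In the event of an adverse event necessitating device removal"
- "After disease progression as defined by objective RECIST 1.1 and CA-125 criteria" (both criteria must be met)
- "At the final 18-month post-implantation time point"

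The footnotes to the schedule of assessments, repeated in the SAP flowchart, allow removal before month 18 when the conditions in Section 6.2 are met. They point to no other section.

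**SAP, classification.** Section 2.5 defines recurrent patients by the reason for removal: progression by both criteria, or a reason recorded as other "that indicates recurrence". Non-recurrent patients "are the remaining patients". The definition sets no condition on removal reason, dwell time or length of follow-up.

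**SAP, use.** Non-recurrent patients are sub-population (3) of the primary performance analysis (2.4.5) and of the focalization analyses (2.4.6, 2.4.7). In 2.4.7 the Kaplan-Meier analysis of time to recurrence censors, at the date of removal, anyone whose device is removed before 18 months for a reason other than recurrence.

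**The concern.** There are two separate issues.

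The first is operational. A patient may withdraw during chemotherapy. Section 6.7.2 then calls for removal before exit, while 6.2.3 places removal after chemotherapy and does not mention withdrawal. Neither section says what happens if the patient withdraws and declines the operation. A site would have to settle both questions without guidance, and the procedure is a laparoscopy for which the protocol foresees possible conversion to laparotomy.

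The second is analytical. A patient explanted at month 4 on withdrawal has an unknown recurrence status at month 18. SAP 2.5 nevertheless counts her as non-recurrent, together with patients observed without recurrence to month 18. Capture is evidence that builds up while the device is in place, so the non-recurrent capture rate would mix different exposure times. It would also mix patients known to be free of recurrence with patients who were simply not observed long enough.

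**Working it through.** **1. The plan's own figure.** The sample size is n = 20 for 90% against 65% (90% minus the 25-point margin), one-sided alpha 0.05, power above 85%. The exact binomial rule of success at 17 or more of 20 gives alpha 0.044 and power 86.7%, so the figure reproduces. The 22 treated patients follow from 20 × 1.10 = 22. This point does not depend on the sample size; only the dropout allowance is used below.

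**2. The passages side by side.**

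| Question | Protocol 6.7.2 | Protocol 6.2.3 and schedule footnotes |
|---|---|---|
| Is withdrawal a reason for removal? | Yes, if still implanted | Not listed; early removal is tied to Section 6.2 |
| When? | Before exit, at any time | After chemotherapy |
| Patient declines removal? | Not addressed | Not addressed |

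| Patient with device removed before month 18, no recurrence | SAP treatment |
|---|---|
| Time to recurrence (2.4.7) | Censored at removal |
| Capture and focalization by sub-population (2.5) | Non-recurrent |

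The second table also applies to a removal for an adverse event. Protocol 6.2.3 keeps such a patient in follow-up to 18 months, but SAP 2.5 classifies by removal reason, so a recurrence after that removal would not change her class.

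**3. Possible size.** Inputs: 22 As-Treated patients; 10% dropout (Protocol 10.1, SAP 2.2), so 10% of 22 = 2.2, taken as 2; about 40% to 50% progressing by 12 months (Protocol 1.5). Assumption: both dropouts are withdrawals with explant and without recurrence.

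- *12-month rates, not extrapolated.* Recurrent: 22 × 0.40 = 8.8, taken as 9, or 22 × 0.50 = 11. Remaining: 13 or 11. Share of withdrawal explants: 2/13 = 15% or 2/11 = 18%.
- *Constant hazard to 18 months, applied to the other 20 patients.* Free of progression: 0.60^1.5 = 0.465 or 0.50^1.5 = 0.354. Non-recurrent at month 18: 20 × 0.465 = 9.3 or 20 × 0.354 = 7.1. Share: 2/(9.3 + 2) = 18% or 2/(7.1 + 2) = 22%.

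The range is about 15% to 22%.

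**4. Effect on a capture rate (illustration).** Suppose neither withdrawal explant contains tumor cells. The exact one-sided 90% lower bound for x of n is the 10% quantile of Beta(x, n − x + 1).

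| Withdrawal explants excluded | Included |
|---|---|
| 6/11 = 54.5%, lower bound 31.8% | 6/13 = 46.2%, lower bound 26.4% |
| 4/9 = 44.4%, lower bound 21.0% | 4/11 = 36.4%, lower bound 16.9% |

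The assumed capture counts are not in the documents. They show only that two patients can move the estimate by about 8 points and the bound by about 4 to 5.

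**The case against.** Much of the opposing case stands.

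- **The two protocol sections can be read together.** 6.2.3 can be taken as the rule for patients who stay in the study, and 6.7.2 as an added provision for those who leave. Nothing in 6.2.3 forbids removal on withdrawal. A reader might infer a flat contradiction, or that surgery is imposed on an unwilling patient. The text supports neither: 6.7.2 places removal before exit and does not say that it proceeds over a refusal. The consent pages were removed from the review copy, so what patients are told cannot be judged. What remains is the timing mismatch, footnotes that cite Section 6.2 only, and the missing route for refusal.
- **The CRF is not among the documents.** A reader might infer that it has no withdrawal option. That cannot be shown. Only the derived recurrent/non-recurrent split is shown to lack one.
- **Related outputs are already planned.** Tables 88 and 90 give duration until removal and reasons for removal. Listings 22 and 26 cover the primary performance endpoint and removal information. With at most 22 patients, withdrawal explants could probably be picked out by hand. That helps a reader of the listings but does not change the sub-population result as defined.
- **A larger share is tempting.** Extrapolating progression to all 22 leaves 22 × 0.465 = 10.2 or 22 × 0.354 = 7.8 non-recurrent, and two withdrawals look like a fifth to a quarter. That applies the hazard to the withdrawals and then counts both of them among the non-progressors. Even 15% to 22% is an upper case: dropouts who are lost to follow-up need not yield an explant. Removal for progression requires both RECIST and CA-125 criteria, which could enlarge the non-recurrent group and lower the share.
- **Not every withdrawal is early.** A month-15 withdrawal is not a short dwell. The SAP rule is indifferent to dwell time, which is the point at issue.

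**Conclusion.** The point holds in a limited form.

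On the protocol, 6.7.2, 6.2.3 and the schedule footnotes leave a gap on timing and on refusal, and they must be reconciled. Which rule should apply is not a matter for this review.

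On the SAP, the non-recurrent class is a catch-all. It treats patients whom the SAP itself censors in the time-to-event analysis as non-recurrent in one of the three primary-performance sub-populations and in the focalization analyses. The cause is not specific to withdrawal, since early adverse-event removals fall into the same class. With both dropouts assumed to be withdrawals with explant, the share is about 15% to 22% of the non-recurrent group; with fewer such explants it is smaller.

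A reader might infer that the main performance result is compromised. It is not: Protocol 10.3 defines the primary performance endpoint in recurrent patients only, and no hypothesis test is attached to the non-recurrent sub-population. The SAP's overall As-Treated capture figure would include these explants, but it covers the whole population and makes no claim about recurrence status.

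**What to change.** **Protocol.** The sponsor should reconcile 6.7.2, 6.2.3 and the schedule footnotes so that one instruction covers a patient who withdraws while implanted, including withdrawal before chemotherapy ends and withdrawal with removal declined. The content of that instruction is for the sponsor and the ethics committee.

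**SAP 2.5.** Limit non-recurrent to patients followed without recurrence to the month-18 removal. Place explants done earlier for withdrawal, an adverse event or another non-recurrence reason in a separate class, reported with dwell time. Alternatively, keep the present definition and add a sensitivity analysis that excludes them. Either option brings the sub-population analyses into line with the Kaplan-Meier censoring rule. The sponsor should also confirm that the CRF records withdrawal as a reason for removal.

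**Cost.** Protocol wording, a line or so in SAP 2.5 and an extra column in the affected tables. The statistical downside is a smaller non-recurrent group, with wider confidence bounds at a given capture rate.

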## 8. ADVERSE EVENT MANAGEMENT

### 8.1. Event Definitions

Subjects will be carefully monitored during the study for possible Adverse Events (AEs) from the time the Subject signs the Patient Informed Consent form to the completion of their participation in the study. Any AE observed will be fully investigated by the Investigator and classified in line with the definitions of the ISO 14155:2011 below.

**Adverse Event (AE):** Any untoward medical occurrence, unintended disease or injury, or untoward clinical signs (including abnormal laboratory findings) in subjects, users or other persons, whether or not related to the investigational medical device

NOTE 1 This definition includes events related to the investigational medical device.

NOTE 2 This definition includes events related to the procedures involved.

NOTE 3 For users or other persons, this definition is restricted to events related to investigational medical devices.

**Device Deficiency:** Inadequacy of an investigational medical device related to its identity, quality, durability, reliability, safety or performance. This may include malfunctions, use error, or inadequacy in the information supplied by the manufacturer.

**Adverse Device Effect (ADE):** Adverse event related to the use of an investigational medical device.

NOTE 1 This includes any adverse event resulting from insufficiencies or inadequacies in the instructions for use, the deployment, the implantation, the installation, the operation, or any malfunction of the investigational medical device.

NOTE 2 This includes any event that is a result of a use error or intentional abnormal use of the investigational medical device.

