The investigator will document all AEs on the Adverse Event Form, including (at a minimum) a description of the event, date of onset, severity, relationship to the investigational device and/or procedure, required interventions, duration, and outcome. The investigator will monitor all AEs until they are resolved, determined to be a chronic condition or the subject is lost to follow-up. The investigator will report all AEs regardless of whether it is anticipated or unanticipated and regardless of classification, seriousness, intensity, outcome or causality.

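### Protocol 6.7.2 does not separate withdrawal of consent from discontinuation by the investigator, and on its natural reading ends data collection for both, so later safety events can be lost in a direction that favours the device

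*Protocol*

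**What the plan says.** Protocol 6.7.2 covers two routes out of the study. The patient may withdraw at any time. The investigator may discontinue her if she can no longer fully comply, or "if any of the study procedures are deemed potentially harmful to the subject". The next sentence gives one data rule: what is already on record for withdrawn subjects is kept and analysed, but "no new data will be collected after withdrawal". Patients still implanted when they intend to withdraw "will undergo the device removal procedure and associated assessments before being exited from the trial". The section closes with "Withdrawn subjects will not be replaced".

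Three other places bear on the same patient:

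- Protocol 8.4: "The investigator will monitor all AEs until they are resolved, determined to be a chronic condition or the subject is lost to follow-up".
- Protocol 8.1: adverse events are monitored "from the time the Subject signs the Patient Informed Consent form to the completion of their participation in the study".
- Protocol 6.2.3: "All patients will be followed through 18 months, regardless of whether or not the device was removed at an earlier time point".

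On scoring, SAP 2.5 classes a patient as not free of MAEs if a qualifying event is recorded within 6 months ± 2 weeks of implantation, and as free otherwise. It requires no minimum follow-up. The opening line of SAP 2.5 sets a derived criterion to missing when an item needed for it is missing. SAP 2.1.2 plans no imputation, and SAP 2.1.3 computes percentages on non-missing observations.

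**The concern.** Withdrawn consent can justify a full stop to data collection. A decision by the investigator is different, because the patient may still agree to her data being used. One of the investigator's two grounds is a safety ground, so stopping may well be related to the outcome being measured.

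A site with a discontinued patient and an open adverse event gets different instructions from 6.7.2 and 8.4. If it follows 6.7.2, it records no MAE that begins after exit but inside the 6-month window, no outcome for an open event, no later progression and no later death. The primary safety test, the mortality rate (SAP 2.4.6) and the time-to-recurrence curve (SAP 2.4.7) all draw on those data. The analysis at 6 months is meant to support CE-marking. With about 20 patients, one event can matter.

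**Working it through.** **1. The text, for a patient discontinued by the investigator with an open adverse event**

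| Section | Instruction |
|---|---|
| Protocol 6.7.2 | No new data after withdrawal |
| Protocol 8.4 | Monitor until resolved, chronic or lost to follow-up |
| Protocol 8.1 | Monitor until participation is complete |
| Protocol 6.2.3 | Follow all patients to 18 months, even after early device removal |

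Lost to follow-up has its own criteria in 6.7.1 (three consecutive missed visits, three failed contact attempts and a letter to the sponsor). A discontinued patient does not meet them simply by being discontinued. So 8.4 keeps her record open while 6.7.2 closes it, and 8.1 points towards closing it.

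**2. The plan's own sample size**

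Inputs (Protocol 10.1, SAP 2.2): expected freedom from MAE 90%, margin 25 points, so the null is 90% − 25% = 65%; one-sided alpha 0.05; n = 20; power above 85%; 10% dropout; 22 treated.

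The exact one-sided p for x MAE-free of n is the sum over k = x to n of C(n,k) × 0.65^k × 0.35^(n−k).

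- 17/20: p = 0.044, pass. 16/20: p = 0.118, fail.
- Power at 90%: P(X ≥ 17 | n = 20) = 0.867, which agrees with the stated figure.
- 20 × 1.1 = 22 treated.

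**3. The largest number of MAEs that still passes**

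| Patients analysed | MAE-free needed | MAEs allowed | Exact p at the limit |
|---|---|---|---|
| 22 | 19 | 3 | 0.025 |
| 21 | 18 | 3 | 0.033 |
| 20 | 17 | 3 | 0.044 |
| 19 | 17 | 2 | 0.017 |

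From 22 down to 20 patients the limit stays at three. Dropping a patient with an unseen MAE therefore removes an event without tightening the limit.

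**4. Illustration: 22 treated, 4 true MAEs, one after exit (assumed counts)**

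| Handling | Result | Exact p | Test |
|---|---|---|---|
| Complete data | 18/22 | 0.072 | fail |
| Unseen, scored MAE-free | 19/22 | 0.025 | pass |
| Unseen, set to missing | 18/21 | 0.033 | pass |

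With 5 true MAEs and 2 unseen the pattern is the same: 17/22 (p = 0.163) fails, while 19/22 (p = 0.025) and 17/20 (p = 0.044) pass.

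**5. Dependence on the form of the test**

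SAP 2.4.5 names a one-sided one-sample binomial test and an exact interval, but does not say that the test itself is exact. Under the normal approximation, z = (x/n − 0.65) / √(0.65 × 0.35 / n):

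- 18/22: z = 0.1682/0.1017 = 1.654, p = 0.049, which just passes.
- 17/22: z = 0.1227/0.1017 = 1.207, p = 0.114, which fails.
- 17/21: z = 0.1595/0.1041 = 1.533, p = 0.063, which fails.

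The tipping point then moves to five true MAEs. One unseen event still reverses the result if scored free (17/22 becomes 18/22), but not if set to missing (17/21).

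**The case against.** **The bar is not expressly applied to discontinued patients.** The data rule speaks of withdrawn subjects, the investigator's act is called discontinuing, and the heading of 6.7 names the two separately. A reader might infer that the protocol plainly forbids data on patients taken off for harm. It does not: the ground is potential harm, and the bar reaches these patients only by context. The context is strong, since the rule follows directly and no other rule is given for them. If that reading is not intended, the text is ambiguous and needs the same clarification.

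**The contradictions can be overstated.** The 18-month sentence in 6.2.3 addresses early device removal, not study exit, and a withdrawal section may limit a general rule. It sits uneasily with 6.7.2 but does not flatly contradict it. Section 8.1 lets 8.4 be read as covering only patients still participating. What stands is that 8.4 lists its own end points and withdrawal is not among them.

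**Much is still captured.** Events recorded before exit are kept, and patients still implanted have removal and its assessments first. An infection already on record that leads to device removal can still count in the primary endpoint. A lost primary event must start after exit, fall within the window and be device- or procedure-related. Several listed components, such as prolonged intubation, are mainly perioperative. This narrows the loss but does not remove it.

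**The reversal is not universal.** A reader might infer that at n = 20 one unseen event always turns 16/20 (p = 0.118) into 17/20 (p = 0.044). That needs the MAE-free default. If the patient is set to missing, the exact result is 16/19, p = 0.059, which still fails. The 20 are also the evaluable patients after dropout, so an early exit would more naturally fall among the other two. Starting from 22 treated, the exact test reverses under either handling.

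**Conclusion.** The point holds as a gap to be reconciled with a one-directional effect on the safety results. An MAE that is not collected cannot raise the MAE count, and neither scoring route in SAP 2.5 charges it to the device. Near the decision limit one unseen event is enough: with 22 treated and 4 true MAEs, the exact test moves from p = 0.072 to 0.025 or 0.033. Away from the limit the conclusion does not change, although the MAE and mortality rates can still be understated.

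This rests on three assumptions: that 6.7.2 covers investigator discontinuation, that the primary test is exact, and that the event counts are illustrative. The documents give no event rate for discontinued patients, and the 10% allowance covers all dropout. That these patients carry more risk is a reasonable inference from the safety ground, not a documented fact. The consent form is not among the documents reviewed, so whether consent survives discontinuation cannot be confirmed.

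**What to change.** - **Protocol 6.7.2:** limit the stop on new data to patients who withdraw consent to further data collection. For patients discontinued by the investigator, or who only stop attending visits, and whose consent remains, continue to collect from clinic records or by telephone: MAE status to the end of the 6-month window, open adverse events to resolution, progression, and vital status to month 18.
- **Exit form:** add one item recording which kind of withdrawal applies.
- **Protocol 6.7.2, 8.1 and 8.4:** reconcile them so that one end point for adverse event collection applies to each kind of exit. State how the 18-month sentence in 6.2.3 relates to study exit.
- **SAP 2.5:** do not score a patient without complete 6-month follow-up as MAE-free by default. State her handling, and add a sensitivity analysis that counts such patients as failures. In the illustration this gives 18/22, the same as complete data.

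The failure count belongs in a sensitivity analysis because it is severe. With 2 of 22 counted as failures, 19 of the other 20 must be MAE-free, which has probability 0.392 at a true rate of 90%. Collecting the data is the better protection.

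The cost is protocol wording, consent wording if needed, one form item, a little site time for record review and slightly more analysis work. No procedures or patients are added.
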